## **2a. Research Plan**

### **Background and Significance**

Traumatic brain injuries (TBIs) inflict an enormous toll on military personnel (Warden, 2006). TBI related impairments in goal-directed behavior can have a significant impact on social and occupational functioning. Common complaints include difficulties with holding information in mind, distractability, performing multiple tasks simultaneously, and feeling easily overwhelmed (Kennedy et al., 2008; Church, 2009; Chen & Loya, 2014). These cognitive difficulties are often exacerbated by symptoms of post-traumatic stress (PTS; Vasterling et al., 2009; Polak et al., 2012; Scott et al., 2015). An underlying source of these complaints relates to brain functions important for the goal-directed regulation of attention, learning, memory and organization (Larson et al., 2006; Chen et al., 2011, 2012). Veterans hampered by deficits in these areas may not learn as quickly or perform as effectively as they did prior to their injuries. There remains a major need for interventions specifically designed to improve goal-directed functioning.

The path towards developing improved interventions for these cognitive challenges may be aided by a rehabilitation neuroscience approach. This approach elucidates neural-behavioral mechanisms of improvements in cognition, and leverages that knowledge to improve existing interventions or develop novel ones. As an intermediate step in this developmental process, appropriate neurophysiological measurements should be included to probe mechanisms of training-induced plasticity associated with existing interventions targeting improved functioning. Ideally, interventions and measurements should draw from a unified neuroscience framework to facilitate empirical tests of theory.

To promote improvements in goal-directed functioning, we have developed a series of interventions (Chen et al., 2011; Novakovic-Agopian et al., 2011; Loya et al., 2014; Rodriguez et al., 2014). Training emphasizes learning the goal-directed application of self-regulation skills across multiple challenge contexts. Participants are trained in applying a Stop-Relax-Refocus (S-R-R) strategy to stop activity when distracted or overwhelmed, relax, and redeploy attentional resources for the task at hand. To facilitate the transfer of these skills to daily life, we developed scenarios that allow for greater intensity of practice across a wide range of challenging contexts. These scenarios were implemented in digital game format to increase access to well-designed and calibrated learning opportunities. Trainers provide intensive, individualized coaching that maximizes each patient's understanding of trained skills, strengthens skill use, and develops the ability to strategically apply these skills in situations outside the training environment. In sum, challenging experiences are integrated with coaching to provide intensive guided experiential learning. Thus, the intervention utilized in the proposed study will intensively train self-regulation skills via extensive and supported practice with their application across a continuum of simple to complex contexts and goals.

There is significant variability in response to any given rehabilitation intervention, and the neural bases of this variability are not well understood. Electroencephalography (EEG) is a research tool with an established history of clinical application following TBI (Rapp et al., 2015; Schmitt & Dichter, 2015). Previous reports of mild to moderate TBI have suggested alterations in the theta (4-8 Hz) and alpha (8-13 Hz) ranges (Thornton & Carmody, 2009). Given its availability in clinical settings, and utility in measuring the effects of attention and working memory (Luck et al., 2000), we propose to examine the neurophysiologic underpinnings of behavioral responses to training using well-validated event-related EEG markers, and novel application of EEG network connectivity measures to resting state data. In a related example, EEG markers for Attention-Deficit Hyperactivity Disorder (ADHD) suggested that processing deficits in the encoding and maintenance stages of working memory (WM) are differentially explained by variance in theta and alpha (Lenartowicz et al., 2014). Application of these methods to understand and even predict treatment outcomes could help direct interventions, save time, and improve patient quality of life. Better understanding the neural bases of functional improvements may help guide intervention development by providing new markers for feedback or targets for electrical modulation.

We will use a novel combination of neurocognitive training and two categories of EEG data for these investigations. (a) Event related changes in brainwaves can dissociate components of working memory into discrete processes that are targeted by training (attention, encoding, maintenance). We will examine EEG with WM load under distraction pre- and post-training, and test whether these markers help to explain neural bases of variability in behavioral changes with training. We predict that training-induced changes in

working memory span and attention/executive functioning will be related to changes in established EEG markers. (b) Network connectivity models of dynamic brain networks will be synthesized from brief assays of tonic self-regulation. Our previous work has shown that baseline network modularity during a brief period of self-regulation, as measured by functional MRI, can predict response to cognitive training (Arnemann et al., 2015). In the current project, we will evaluate the use of EEG network connectivity analysis to predict response to cognitive training. Measures of brain network properties do not rely on averaging individuals with different anatomy (Tymofiyeva et al., 2014), and therefore may be particularly useful for real-world applications.

## Preliminary Studies

Our preliminary data support the component foundations for the project, including the feasibility of implementing the proposed intervention; a model for determining the extent of neural changes; and the plausibility of the hypothesized mechanisms, with data to ground power calculations for testing these mechanisms.

(1) Goal-oriented attentional self-regulation training (GOALS) for Veterans with chronic TBI: In an ongoing study, 32 Veterans with chronic TBI and functional complaints received GOALS or brain health education (BH) training, matched for time and intensity over 5-6 weeks. Pre-to-post-training changes on a composite measure of attention and executive functions ( $p < 0.01$ ), as well as on a simulated, ecologically-valid 'real-world' task ( $p < 0.01$ ) were observed following GOALS and not BH. These data support the potential value of training Veterans with TBI how to better self-regulate within the context of their individual goals.

(2) Guided experiential learning of goal-oriented self-regulation (intensive skill training supported by digital game experiences): Extending this work, we developed methods to provide more intensive training in the strategic application of self-regulation skills. This system was designed to "bridge the gap" between initial skill learning and transfer of skills to personal life (Loya et al., 2014, submitted; Rodriguez et al., 2014). In ongoing studies, 19 participants with history of brain injury and chronic cognitive symptoms have completed 7 training sessions in person or by tele-video, and approximately 30 minutes of daily practice over 6-8 weeks using custom-developed digital game experiences ('From Startup-to-CEO'). Objective measures of transfer to performance on non-trained tasks have been obtained using a range of measures. In preliminary analyses, improvements have been documented on composites of complex attention and executive functions ( $t(18) = 2.66, p = 0.016, d = 0.63$ ), verbal learning and memory ( $t(18) = 2.02, p = 0.06, d = 0.48$ ), and processing speed ( $t(18) = 2.99, p = 0.008, d = 0.71$ ). These results provide a promising foundation for training Veterans with brain injury and will allow investigation of the neural bases of improvements in cognitive functioning.

(3) Functional brain network organization and learning in response to training: The ability to regulate 'baseline' brain state likely influences performance during goal-directed cognitive tasks (Otten et al., 2006; Guderian et al., 2009). Brain state can be described by network parameters such as the modularity of brain network organization. Modularity is theorized to support learning and plasticity by enhancing the adaptivity, robustness, and evolvability of network function (Stevens et al., 2012). Modularity is a summary of the extent to which a large-scale brain network can be characterized by sub-networks (i.e. modules) with high within-module connectivity, and low between-module connectivity. We posited that parameters of brain state such as modularity may 'tune' how the brain handles tasks, influencing the responsiveness, efficiency, and plasticity of brain networks in response to experiences. As an initial test, we examined the extent to which network modularity might explain inter-individual variability in response to cognitive training for TBI patients ( $n=11$ ) who participated in GOALS training (Arnemann et al., 2015). We acquired fMRI from brief pre-training sessions, in which patients were instructed to try to achieve a relaxed but focused resting state (an assay of brain state regulation). We examined the predictive value of baseline modularity during this 'focused rest' assay for pre- to post-training changes in measures of attention and executive control. Pre-training brain modularity predicted the degree of improvement in attention/executive function following training (*Pearson correlation r=0.61m p<.05*), such that those individuals with higher baseline modularity exhibited greater treatment response. These results provide preliminary support for the hypothesis that the regulation of functional brain network organization may influence learning. In the present proposal, we will use EEG in a similar manner to characterize network modularity before and after training.

(4) ERP measures of working memory and multitasking: Key elements of the training program aim to improve attention regulation as a gateway for working memory and the ability to multitask. Laboratory

measures of these cognitive functions have been studied using EEG recording (Gazzaley, 2011; Pratt et al., 2011). Our recent work demonstrated that Veterans with mild TBI and PTS showed a working memory deficit when cognitive control functions were more heavily taxed (Honzel et al., 2014). In that study, we examined working memory for letters maintained across a delay that was either unfilled, or filled with a challenging distractor task. The patients were slightly less accurate than controls on the unfilled (single task) version, but impaired to a disproportionate extent on the dual task version. Furthermore, a neural index of memory retrieval processes was unaltered in the patients for the single task version but decreased for the dual task (*difference wave at Cz, dual task:  $t(30)=2.704, p=.011$ , Cohen's  $d=.956$* ). This event-related potential (ERP) "old/new" effect differentiates correctly remembered old items from correctly rejected new items, beginning at 300 ms post-stimulus and continuing for several hundred ms (Rugg & Curran, 2007). This task will allow us to assess brain activity and task performance before and after training, to test the prediction of an increase in the ERP old/new effect after training.

## Research Design and Methods

**Participants:** The participants will be Veterans with history of TBI:  $n = 20$  will undergo the training intervention, and  $n = 20$  will participate in repeated testing without intervention. Inclusion criteria: Veterans, ages 21 to 55, with a history of TBI (as defined by the American Congress of Rehabilitation Medicine and VA, with reported plausible mechanism of head injury, loss of consciousness with some period of post-traumatic alteration in cognition), in the chronic, stable phase of recovery ( $>6$  months from injury), with residual cognitive complaints (Neurobehavioral Symptom Inventory, cognitive subscale  $>9$ ). Participants will be on stable psychoactive medications ( $> 30$  days); able and willing to participate in EEG, training and, assessments. *Common mental health comorbidities present amongst OEF/OIF/OND Veterans, such as depression and PTS (Carlson et al., 2011; Carter, 2014), will be permitted in order to address realistic aspects of recruitment (i.e. it would be unrealistic to expect a sample of 'pure TBI' amongst current generation combat Veterans) as well as a practical goal of intervention work in addressing needs of Veterans. However, participation will be limited to Veterans reporting PTS and depression symptoms below clinical thresholds (see self-report questionnaires section for more details: PCL-5 scores  $< 38$ , Weathers et al., 2013; BDI-II scores  $< 19$ ; Homaifar et al., 2009).* Exclusion criteria: Severely apathetic/abulic, aphasic, or other reasons for being unable or unwilling to participate with the training tasks; severe cognitive dysfunction; history of neurodevelopmental abnormalities; ongoing illicit drug or alcohol abuse (AUDIT $>8$ ); schizophrenia; bipolar disorder; history of other neurological disorders; current medical illnesses that may alter mental status or disrupt participation in the study; active psychotropic medication changes. There will be no restriction in regard to gender, race and socioeconomic status.

**Study design and participant flow.** Participation in the proposed study will span approximately 10-12 weeks. Participants will be recruited via IRB-approved methods, and interested candidates will undergo preliminary screening ( $\sim 1$  hr phone interview + VA records review). Eligible participants will be invited to enroll and provide informed consent approved by the IRB of VA Northern California.

Baseline assessments of cognitive status and functioning, as well as EEG, will be conducted in weeks 1-2. Time commitment for baseline assessments is approximately 4-5 hours. Participants will then be assigned to (a) active training or (b) no training conditions in a pseudo-random order, matched across key demographic variables. The no training condition will serve to assess changes to EEG and other measurements with repeated testing in the absence of active training. This will lay a foundation for future studies that will incorporate an active comparison intervention.

Participants in active training will complete seven training sessions in weeks 3-10. Training sessions last 2 hours, and participants are requested to complete approximately 2.5 hours of additional skill practice over the course of each week outside of session (total  $\sim 4.5$  hours per week). The same overall training time will be targeted ( $\sim 32$  hours) for all individuals, although the training schedule will accommodate variations in individuals' schedules and availability over the course of  $\sim 8$ -10 weeks to maximize engagement. In the 2 weeks after training concludes, participants will complete a second round of assessments ( $\sim 3$ -4 hrs). Participants will be compensated \$20/hr for their time during the assessment portions of the study as well as for their travel expenses at \$0.55/mile for travel greater than 20 miles to and from the study site.

Enrollment will begin within 3 months of the initiation of the grant period, and continue through month 21. Data will be checked and pre-processed on a rolling basis and final analyses and reports will be completed in months 22-24.

**Training Intervention:** Training follows a manualized protocol, with seven in-person two-hour sessions (Loya et al., 2014; Rodriguez et al., 2014) and instructions to practice skill use while playing the Startup-to-CEO game for 30 minutes/day, five times per week, and to practice skill use within the context of their daily life. Game scenarios are utilized to highlight contexts where goal-directed functioning is susceptible to disruption and where skill use might be helpful. They further help facilitate discussions about skill application in personal life. In addition, twice weekly semi-structured phone check-ins are conducted to provide motivational support and reinforce skill use.

**Pre- and Post-training Assessments of Neuropsychological Performance:** Standardized tests will be administered before and after training (Novakovic-Agopian et al., 2011). The Assessor will be blind to treatment status. All instruments have well-established psychometric properties, and many are included in NINDS Common Data Elements for TBI (indicated with “\*”). Attention and executive function will be assessed using Letter Number Sequencing\* (WAIS-IV); Auditory Consonant Trigrams; Digit Vigilance Test; Design and Verbal Fluency Switching; Trails B\*; DKEFS\* Color-Word Interference: Inhibition and Inhibition/Switching subtests (Delis & Kaplan, 2001). To account for practice effects, alternative test forms will be used when possible, and/or norms for repeated testing will be used. The major outcome measures will be a composite score (averaged z scores) of the attention/executive function domain (Arnemann et al. 2015) and the Automated Operation Span Task, which assesses WM in the presence of distractions (Unsworth et al., 2005). Training effects on primary outcomes will be assessed by computing pre-post change scores. Participants will complete questionnaires of self-perceived changes in cognitive functioning.

**Self-Report Questionnaires:** Each participant will be given two additional questionnaires to assess psychological symptoms as potential covariates. The PCL-5 is a 20-item self-report measure of DSM-5 PTSD symptoms used for screening or monitoring symptoms of PTSD (Weathers, et al., 2013). A *cut-off score of 38 has been recommended as a threshold for diagnosis of PTSD (Weathers et al., 2013)*. The Beck Depression Inventory (BDI) is one of the most commonly used self-reported screens for major depressive disorder. *A cut-off score of 19 has been used as a threshold for major depressive disorder for Veterans with mild TBI history (Homaifar et al., 2009)*. Participant replies will be monitored for suicidal ideation or intent. If there is any indication that a participant is a danger to self or others, a protocol has been established to ensure that he or she will be further evaluated by [name] or [name] to determine what level of intervention is necessary. VANCHCS Mental Health Service provides emergency walk-in evaluations, if it is believed that immediate or a greater level of intervention is necessary. In addition, all participants are provided information about the Suicide Hotline number for Veterans ([name]).

**Pre- and Post-Training EEG:** Participants will attend testing sessions pre- and post-training. The first phase of each session measures several minutes of resting state brainwaves for use in connectivity modeling (Langer et al., 2013). Participants will complete a brief assay of self-regulation, with instructions to relax and focus on the cycle of breathing, re-directing attention if the mind wanders, as in our prior fMRI study (Arnemann et al., 2015). In the second phase, participants will perform our well-validated working memory dual task while EEG is recorded and averaged using standard methods. EEG time-frequency analyses will target the theta and alpha bands based on prior studies (Thornton & Carmody, 2009). This experiment is ideal for use in evaluating potential neural mechanisms of our targeted training, because of its sensitivity to working memory load and distractions. Data will be collected by staff in [name] lab, and EEG analysis carried out by [name], who has experience describing EEG markers and evaluating novel training approaches in clinical populations (Pineda et al., 2014).

**ERP Recording:** Continuous EEG will be recorded from 64 scalp electrodes and two electrodes placed on the left and right mastoids using the ActiveTwo Biosemi electrode system. Four electrodes placed laterally and below both eyes will record blinks and eye movements. The EEG will be sampled at 512 Hz. Biosemi uses a “common mode sense” active electrode and “driven right leg” passive electrode to form a feedback loop that serves as the “ground” electrode. All signals will be recorded using ActiView software.

**ERP Data Analysis:** Off-line analysis will be completed using Brain Vision Analyzer software. Data will be re-referenced to the average of the mastoid electrodes and bandpass filtered from 0.1 to 30 Hz (48 dB/octave). The EEG will be segmented for each trial beginning 100 ms pre-stimulus and extending to 900 ms post-stimulus onset. EEG will be corrected for blinks using the Gratton procedure; artifacts exceeding 150  $\mu$ V will be rejected. Segments will be baseline corrected and averaged with similar trials. ERPs will be

quantified by computing mean amplitudes in defined latency windows relative to a 100 ms pre-stimulus baseline. The primary measure will be the ERP “old/new effect” elicited during memory retrieval, time-locked to probe onset. This will be quantified by subtracting mean amplitude for Old – New probes (300-500 ms post-stimulus) at midline electrodes (Honzel et al., 2014).

**EEG Time-Frequency and Network Analysis:** Off-line analysis for resting state and dual task data will be performed in the EEGLAB Matlab toolbox (Delorme & Makeig, 2004). Data will be filtered with bandpass limits of 0.1 to 55 Hz using a standard FIR filter and re-referenced to the average of mastoid electrodes. Periodic artifacts, such as eyeblinks, will be removed using the Infomax Independent Component Analysis (ICA) algorithm. Remaining data will be further band filtered into four frequency bands (theta: 4-8 Hz, alpha: 8-13 Hz, beta: 15-30 Hz, & gamma: 30-55 Hz), and power envelope and phase angle will be extracted with a Hilbert transform.

Resting state connectivity will be calculated over two second epochs using a graph theoretical approach comparing each pair of electrodes in each frequency band, based on correlation of band power changes, and degree of phase coherence. *As we are working with resting state data, we have no a priori hypothesis about directionality of information flow. Therefore, correlations of these measures will suffice (Bastos & Schoffelen, 2016), thereby decreasing computation demands.* Spurious connectivity will be corrected by eliminating neighboring electrode connections and ignoring electrode pairs with 0 degrees of phase lag. Remaining electrode pairs will be adjusted to a common threshold to control number of network connections across patients. From these binarized connectivity matrices, modularity and characteristic path length (CPL) will be calculated using the Matlab toolbox, EEGNET (Hassan, et al. 2015). Time-frequency responses to dual task conditions will be calculated using Hilbert transformed data, epoched and averaged over the same time window and baseline as ERP analysis.

**Sample Size Calculation:** We powered the study based on prior group differences (mtBI/PTS vs. Controls). We used data from the Sternberg task (Honzel et al., 2014) to obtain an estimate of the standard deviation of the ERP old/new effect, and expected effect size based on a mixed effects ANOVA (subject as random effect) with group as the sole explanatory variable. To estimate sample size, we used the two sample *t* test as an approximation to the mixed effects ANOVA and used the method of variance inflation to account for the additional subject factors (Hsieh et al., 2003). We powered based on the primary experimental question at 80% and will control false discovery rate at 5% (Benjamini & Hochberg 1995) at the time of analysis for tests of other design and subject factors. The Sternberg data showed a mean difference between the patient and control groups of -1.097 with residual error of 0.956 from the mixed effects ANOVA. Using these values in a two-sample *t* test for mean difference, to obtain 80% power we need a sample size of 13 per group. *This pilot study will allow us to collect data to inform power calculations for future studies.*’

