**Dual-Task Condition (Sternberg Memory Task + Arrow Flanker):** Participants will be required to perform the arrow flanker task during the delay interval of the Sternberg memory task. Nine flanker trials begin 300 to 500 ms following the presentation of each memory set. The stimulus parameters are the same as for the single-task flanker. The Sternberg probe is then presented 500 ms following the final flanker trial, and participants respond to indicate whether this item was in the previous memory set.

**Statistical Analysis:** The ERP old/new effect will be analyzed using a mixed effects ANOVA controlling for task (single, dual), set size (one, four), and time point (pre, post). The primary neuropsychological outcome measures will be included in the models as appropriate to assess changes from pre- to post-training. To examine the effects of repeated testing, differences in ERP mean amplitudes between patient groups (trained, untrained), task, and set size will be also be tested using a separate mixed effects ANOVA to control for random effects due to subject. Pre/post differences in Sternberg WM accuracy will be tested using a hierarchical generalized linear model. Time-frequency responses will be analyzed with the same mixed and linear models, with separate calculations for each frequency band, and a repeated measures model including all frequency bands.

**Predicted Results:** We predict that Veterans who show cognitive gains with training (based on neuropsychological measures) will show an increase in the ERP old/new effect in the dual task condition. Additionally, as prior work has shown that WM impairment in ADHD is characterized by decreased levels of alpha power during encoding, and compensatory increases in theta during maintenance (Lenartowicz, et al. 2014), we predict that cognitive gains will be reflected by changes in theta and alpha power over frontal scalp. Importantly, we can determine with precise temporal resolution whether the neural manifestations of training improvements occur during WM encoding, maintenance, and/or retrieval. Additional analyses will determine whether these EEG markers can predict which patients will improve with training.

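### Arms are formed in a matched, pseudo-random order with no stated random element or concealment, and the written between-group model leaves out the matching variables

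*Combined protocol and SAP*

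**What the plan says.** The paragraph on study design and participant flow (Research Design and Methods) is the only description of how the arms are formed. Testing comes first: "Baseline assessments of cognitive status and functioning, as well as EEG, will be conducted in weeks 1-2". Participants are then "assigned to (a) active training or (b) no training conditions in a pseudo-random order, matched across key demographic variables". The planned size is 20 trained and 20 untrained. The matching variables are not named. The plan does not say whether matching is by pair, stratum or minimisation, what pseudo-random means, who holds the sequence, or whether the next assignment is hidden.

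The section on neuropsychological assessments states "The Assessor will be blind to treatment status". That covers outcome assessment; it does not conceal the next assignment.

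The Statistical Analysis paragraph of the working-memory EEG experiment writes out two ERP models. The first is a pre/post model with task, set size and time point, and no group term. The second compares the arms: "differences in ERP mean amplitudes between patient groups (trained, untrained), task, and set size will be also be tested using a separate mixed effects ANOVA", with subject as a random effect. Time-frequency responses use the same models. Neither model names a demographic variable, pair or stratum. The only covariates named elsewhere are the PCL-5 and BDI, introduced as "two additional questionnaires to assess psychological symptoms as potential covariates"; neither is demographic.

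**The concern.** Two separate things are at stake.

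**Allocation.** Assignment follows the full cognitive and EEG baseline, and data are checked and pre-processed as they arrive. Earlier assignments are easy to see, because one arm attends seven sessions with twice-weekly calls and the other does not. The resting-state section predicts that high modularity and low characteristic path length mark the best responders. Nothing written stops the person assigning participants from knowing both the groups so far and the expected predictors of response. The untrained arm is there to show what repeated testing does on its own, so any selection into the arms goes straight into that contrast.

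**Analysis.** Matching removes chance imbalance in the matched variables, so the difference between arms varies less from trial to trial. A model without those variables leaves their variance in the error term and reports a standard error that ignores the gain. The price is intervals that are too wide and lost power in a small trial.

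**Working it through.** **1. The plan's own figure.** Sample Size Calculation gives a difference of 1.097, a residual error of 0.956 and 80% power. Two-sided alpha of 0.05 is assumed, since the plan states no alpha for the primary test.
- Standardised difference: 1.097 / 0.956 = 1.147.
- Normal approximation: n = 2 × (1.960 + 0.842)² / 1.147² = 11.9, so 12 per group.
- Exact t: 12.96, so 13 per group. The stated 13 reproduces.
- Power on these inputs is 80.1% at 13 per group and 94.2% at the planned 20.
- 13 / 12.96 = 1.003, so the 13 contains no visible allowance for the additional subject factors that the section mentions.

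**2. How foreseeable the next assignment is.** This is the best-guess success of someone who knows the scheme and all earlier assignments:
- simple randomisation: 50%
- known blocks of 6: 68%; known blocks of 4: 71%
- matched pairs: (50% + 100%) / 2 = 75%, because the second member of each pair is determined (20 of 40 assignments)
- strict alternation: 100%

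The documents do not say which of these applies.

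**3. Standard error when the matching variables are left out.** Let R² be the share of participant-level outcome variance that they explain. The documents give no value, so a range is assumed. Under close matching, the model SE divided by the true SE is about 1 / √(1 − R²):
- R² = 0.02: 1 / √0.98 = 1.01, type I error 4.8%
- R² = 0.05: 1 / √0.95 = 1.03, type I error 4.5%
- R² = 0.10: 1 / √0.90 = 1.05, type I error 3.9%
- R² = 0.20: 1 / √0.80 = 1.12, type I error 2.9%
- R² = 0.30: 1 / √0.70 = 1.20, type I error 2.0%

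**4. Simulation check.** 20 pairs closely matched on one prognostic score, 20,000 runs per setting, two-sided 5%; unadjusted t test against ANCOVA on the score. Power is at 0.909 SD, the difference detectable with 80% power at 20 per arm.

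| R² | Model SE / true SE, unadjusted | Type I, unadjusted | Type I, adjusted | Power, unadjusted | Power, adjusted |
|---|---|---|---|---|---|
| 0 | 0.3139 / 0.3167 = 0.99 | 5.1% | 5.1% | 80.2% | 80.1% |
| 0.1 | 0.3145 / 0.2987 = 1.05 | 3.8% | 4.8% | 81.1% | 84.0% |
| 0.2 | 0.3150 / 0.2847 = 1.11 | 3.1% | 5.0% | 82.1% | 88.0% |
| 0.3 | 0.3153 / 0.2655 = 1.19 | 2.1% | 5.0% | 84.2% | 91.9% |

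Without matching, the unadjusted type I error stays between 4.9% and 5.1% over the same range. The conservatism therefore comes from matching and then ignoring it. At the plan's own 1.147 SD, power for R² of 0.1 to 0.3 is 94.9% to 96.5% unadjusted and 96.0% to 98.7% adjusted.

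**The case against.** The strongest reply is that the text proves less than it may seem to. Several stronger readings are tempting, and the documents do not support them.

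- **That allocation is predictable.** Pseudo-random and matched are undefined, and could describe minimisation with a random element. The 75% figure needs pairwise matching, which is nowhere stated. What stands is that no protection is described.
- **That demographics are left out of every model.** Sample Size Calculation refers to unnamed subject factors and to tests of other design and subject factors, which might include them. The pre/post ERP model has no group term, and the resting-state correlations and stepwise regression do not compare arms, so the standard-error argument does not reach them. What stands is that the between-group model, as written, names no matching variable.
- **That the untrained arm is the only guard against practice effects.** The neuropsychological tests also have alternate forms where possible, or norms for repeated testing.
- **That omitting the variables produces false positives.** The error runs the other way.

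The size is also open to challenge. Training effects on the primary outcomes are pre-post change scores, in which stable differences in level cancel, so R² may be small. Looser matching on several variables would force less balance than the simulation does. Power at 20 per arm is already about 94% on the plan's inputs, and even the unadjusted figures at 0.909 SD do not fall below 80%, so the loss is a gain forgone. The plan also calls itself a pilot. All of this stands. It makes the covariate half an efficiency point and leaves the allocation half untouched.

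**Conclusion.** The concern holds in two limited parts. First, the plan describes a matched order with no stated random element or concealment, set after baseline data are in hand, so assignment is not protected from being foreseen or steered. This is a risk from an undefined method, not a demonstrated bias, and its degree cannot be fixed from the documents. It is the more important part, because a biased allocation cannot be repaired once participants are enrolled.

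Second, the written trained-versus-untrained model does not reflect the matching. Over an assumed R² of 0 to 0.3 with close matching, the standard error is overstated by 0 to 20%, and type I error falls from about 5% to 2%. Adjustment would add about 3 to 8 percentage points of power at 0.909 SD for R² of 0.1 to 0.3 (84.0 − 81.1 = 2.9; 91.9 − 84.2 = 7.7). At R² of 0.05 or less, or with loose matching, the effect is negligible. Both changes should be made; neither half shows that the comparison is invalid.

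**What to change.** 1. Replace the pseudo-random matched order with a computer-generated sequence: minimisation with a random element, or stratified blocks of varying size. Use the same demographic variables, and name them. State who holds the sequence, and conceal each assignment from the staff who enrol and test participants until that participant's baseline is complete.
2. Add the matching variables as covariates in the models that compare trained with untrained participants: ERP, time-frequency, and neuropsychological change scores where these are compared between arms. Do not add them on this ground to the pre/post model without a group term or to the biomarker correlations and regression.

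The cost is a scripted allocation list, someone outside enrolment and testing to release it, and a few model terms. Demographic balance will be slightly looser than under deterministic matching. Each single-term covariate takes one of the 20 + 20 − 2 = 38 degrees of freedom of a simple two-arm comparison, so three would leave 35. With 40 participants, the list of variables should stay short.
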